## **Subject identification and Recruitment**

We will recruit subjects following inclusion and exclusion criteria mentioned below.

### **Patients:**

Inclusion criteria:

- Subjects will be stroke patients with persistent moderate unilateral lower extremity deficits, age 50-85 years at time of enrollment.
- Time since stroke will be greater than 6 months (“chronic” stroke survivors).
- Persistent moderate unilateral lower-limb impairment (defined as NIH Stroke Scale – Motor Leg section score of 1-2, to be discussed with the patient verbally during phone screening and assessed by the investigator during the initial

enrollment visit).

- Fluent in spoken and written English

Exclusion criteria:

- Allergy to electrode gel, surgical tape and metals.
- Subjects under treatment for infectious diseases will be excluded from the study.
- Women who are pregnant or planning to become pregnant during the course of the study will be excluded.
- Contraindications for MRI
- Age over 85 years at time of enrollment.

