### **Healthy Controls:**

Inclusion criteria:

- Ages 18-85 years
- Non-Stroke Group 1 (“Matched Controls”): 50-85 years old at time of enrollment, to match the population of stroke patients to be studied
- Non-Stroke Group 2 (“Pilot Controls”): 18-50 years old at time of enrollment (Pilot subjects to be initially enrolled early in the design phase of the study, and with enrollment ongoing throughout the study to continue development.)
- No known neurologic, psychiatric or developmental disability.
- Fluent in spoken and written English

Exclusion criteria:

- Allergy to electrode gel, surgical tape, and metals.
- Subjects under treatment for infectious diseases will be excluded from the study.
- Women who are pregnant or planning to become pregnant during the course of the study will be excluded.
- Contraindications for MRI
- Age over 85 years at time of enrollment.

Persons in status relationships with members of the study team may be included in Non-Stroke Group 2 (“Pilot Controls”). Care will be taken to avoid pressuring them to participate. Such steps will include recruitment and guidance in the informed consent process only by study team members who are not in a position of influence over the potential participants.

Recruitment and screening responses from all patients contacted will be recorded in a log for assessment of recruitment yield, to be used in planning recruitment efforts for a later full-scale study. Information to be recorded will include date of contact, eligibility determination, yes/no enrollment, date of enrollment, age, sex, time since last stroke,

and stroke severity. At the conclusion of recruitment efforts for the study, all personal identifying information will be permanently discarded from this log.

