***Subject Identification:***

- Through referrals by the Stroke Neurology team or any clinician involved in patient care, in the in-patient or outpatient setting.
- Clinicians involved in the care of patients may send recruitment letters to eligible patients and ascertain their interest in study participation [email text provided in IRB application].
- Candidates identified for past research in [name] group targeting upper limb therapy may be identified as candidates for this study (if they have lower-limb deficits as well). They will be identified through participant records for protocol #2015-0469 (PI: [name]), which are accessible to [name] as a Co-Investigator on that project.
- We also have permission to contact participants who have participated in other research conducted by our group ([name] 2013-1561). We propose to contact these subjects and ascertain interest in participating as a control subject in this study. Subjects who expressed a written wish not to be contacted for further research (as recorded on their Informed Consent form for protocol - #2013-1561) will be omitted.
- Databases of potential subjects maintained by the UW department of Radiology [[name] #2012-0303 Volunteer Database] may be used to identify healthy control subjects.
- By posting recruitment flyers (for subject self-identification) at different locations such as the UWHC, the School of Medicine, UW libraries, the University Station Clinic, St. Mary's hospital, Meriter hospital, Madison public libraries, stroke support and other aging support group locations, and on the web pages of Principal Investigator [name] (<http://uwbadgerlab.engr.wisc.edu>) and Co-Investigator [name] (<http://vplab.psychiatry.wisc.edu/>).
- [name], who is a radiologist and is involved in clinical imaging protocols of patients, will identify patients who are suitable for study participation as they present to the UWHC, UWMF, WIMR, or Health Emotions Research Institute (HERI) for clinical imaging.

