***Subject Recruitment:***

- [name], who is a radiologist involved in clinical imaging protocols of patients, will recruit patients who are suitable for study participation as they present to the UWHC, UWMF, WIMR, or HERI for clinical imaging or patients who contact him in response to the recruitment flyer. [name] or an authorized member of his staff will invite them to participate in the study.

- Candidates identified for past research in [name] group will be identified through participant records for these protocols ([name] 2015-0469 and [name] 2013-1561). Initial contact will be made by members of the study team of each of those projects. Subjects who expressed a written wish not to be contacted for further research (as recorded on their Informed Consent form for those protocols) will be omitted.
- The study coordinator will be involved in recruiting potential patients referred by the methods above, or patients who contact by telephone or email in response to the recruitment flyer.
- Clinicians involved in the direct care of patients may send recruitment letters to eligible patients and recruit them for the study [recruitment letter attached].
- Recruitment flyers [attached] will be posted at different locations such as the UWHC, the School of medicine, UW libraries, the University Station Clinic, St. Mary's hospital, Meriter hospital, Madison public libraries, stroke support and other aging support group locations, and on the web pages of Principal Investigator [name] (<http://uwbadgerlab.engr.wisc.edu>) and Co-Investigator [name] (<http://vplab.psychiatry.wisc.edu/>).
- Study details will be described to the potential participant by a member of the study team. If the patient expresses willingness to participate in the study, his/her name will be forwarded to the research study coordinator for further follow-up, phone screening, and recruitment according to a screening script [attached in IRB application]. Interested patients may also be asked to directly contact the research study coordinator for further information and screening.
- Participants responding to the recruitment flyer will be contacting the research coordinator. Potential patients will be screened over the phone per the screening script to determine eligibility.

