***Privacy and Confidentiality***

All study procedures are performed in private rooms or research laboratories with closed doors, by staff that have received HIPAA training and in accordance with clinic practice. Subjects may choose not to answer any questions that make them uncomfortable or that they feel violate their privacy. All subject data, including MRI data, will be identified by a subject number. We will take every precaution to protect subject information from a breach of confidentiality with the use of electronic security measures (e.g., passwords). Additionally, paper files will be stored in a locked cabinet when not in use. Subject information will not be disclosed to anyone who is not key personnel on this study without the written permission of the subject. To the extent permitted by law, subject identity and participation in this study will remain confidential.

The subject's name, date of birth, gender, date of MRI scan, and MRI screening form will be obtained for the MRI scan log (participant info form). In addition, information from patient medical records such as medications, medical history, physical exam findings, vitals, radiological data, laboratory data, and procedures will also be collected. These questions are shown in the Health Questionnaire [attached].

The scan logs will be kept in locked cabinets. Only individuals involved with the study will have access to PHI, all identifying information, and all collected datasets which will all be stored in locked cabinets in the PI's office, study coordinator's office, or on password protected computer systems.

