***Study Procedure***

***Subject Assessments***

### ***Behavioral Assessment:***

The following commonly used measures of lower extremity motor assessment, standard stroke scales, and measures of activities of daily living will be administered at starting and ending time points to all patients over the length of the study. Healthy normal controls will complete these measures at the beginning of the study. Pilot controls (enrolled before other groups as well as throughout the study for continuing development) will complete a subset as deemed necessary for preparing the study and the study team for the patient and control groups. The assessments are as follows:

1. Six Minute Walk Test (6MWT): The 6MWT is a simple series of laps along a 30 m straight path in a level hallway. Subjects will be instructed to walk as far as they can in six minutes back and forth along this path, according to standard instructions (Rehab Measures - 6 Minute Walk Test). They will be allowed to use mobility aids, to stop or to rest as necessary. Total distance walked will be recorded based on the number of laps (including any fractional last lap), as well as from the IMU motion reconstruction.
2. Timed Up-and-Go test (TUG): The TUG is a simple timed test of how long it takes to stand up, walk 10 feet, turn around, return to the starting point, and sit down. Subjects will be instructed to perform this sequence as quickly as they safely can, using standard instructions (Podsiadlo and Richardson, 1991). The test will be performed in a laboratory or hallway setting.
3. Self-Selected Walking Speed (SSWS): A simple test of the speed a person chooses to walk over a 5-meter distance.
4. Fastest Comfortable Walking Speed (FCWS): A similar test of the “fastest comfortable speed” a person can use to walk over the 5-meter distance

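### No listed eligibility criterion covers medical fitness for exercise, so the criteria alone do not keep out patients or matched controls with a known contraindication to the pedaling or the six-minute walk

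*Combined protocol and SAP*

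**What the plan says.** The section Subject identification and Recruitment ties enrolment to the lists that follow it: "We will recruit subjects following inclusion and exclusion criteria mentioned below".

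The patient list has four inclusions (age 50–85 with a persistent one-sided leg deficit, more than 6 months since stroke, a score of 1–2 on the leg motor item of the NIH Stroke Scale, fluent English). It has five exclusions, the first of which is "Allergy to electrode gel, surgical tape and metals". The healthy-control list repeats the five exclusions. Its only health inclusion is the absence of a known neurologic, psychiatric or developmental disability. Matched controls are "50-85 years old at time of enrollment, to match the population of stroke patients to be studied".

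On how people reach the study, Subject Identification names clinician referral, letters from treating clinicians, earlier study records, a volunteer database and a radiologist who sees patients at imaging. It also includes an open route: "By posting recruitment flyers (for subject self-identification) at different locations". Under Subject Recruitment, "Potential patients will be screened over the phone per the screening script to determine eligibility"; the script itself is an attachment to the ethics application.

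Health data are gathered. The Health Questionnaire is given to all subjects to document their general health, and Privacy and Confidentiality adds that "information from patient medical records such as medications, medical history, physical exam findings, vitals, radiological data, laboratory data, and procedures will also be collected". Neither place links these data to eligibility.

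On exertion, the Behavioral Assessment section describes the Six Minute Walk Test (6MWT) thus: "Subjects will be instructed to walk as far as they can in six minutes back and forth along this path". Mobility aids and rests are permitted.

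**The concern.** Exercise is the intervention in both arms, and a walk of maximal distance is one of the primary assessments. The population is aged 50–85 and, apart from the matched controls, has had a stroke. A reader would expect at least one criterion on whether a person can safely undertake the exercise. Without one, someone with, for example, a known cardiac contraindication satisfies the lists as written.

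The stake is participant safety. If the criteria are silent, keeping such a person out depends on a script the reader cannot see or on the judgement of whoever makes first contact, and that can differ between recruitment routes. The Benefits section expects no direct short-term gain for participants, while allowing that leg function or cardiovascular health might improve and noting the scientific value of the work. That leaves little individual benefit to weigh against a risk that could be avoided.

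**Working it through.** The plan gives no figure on this point, and the claim does not depend on alpha, power, effect size or sample size. The check is a reading of each listed item against the exercise required.

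**Step 1. Does any criterion concern fitness for exercise?**

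| Item | What it addresses | Fitness for exercise? |
|---|---|---|
| Allergy exclusion | Skin contact with electrodes and tape | No |
| Infectious-disease exclusion | Transmission on shared equipment (Disease Transmission) | No |
| Pregnancy exclusion | Caution about MRI (Pregnancy) | No |
| MRI-contraindication exclusion | Scanner safety | No; it may remove some people with cardiac devices, but only incidentally |
| Upper age limit | Age | No |
| Patient inclusions (4) | Age with leg deficit, time since stroke, leg motor score, language | No |
| Control inclusions | Age bands, neurologic/psychiatric/developmental status, language | No |

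Count: 0 of 5 patient exclusions, 0 of 4 patient inclusions, 0 of 5 control exclusions and none of the control inclusions.

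**Step 2. Is there such a rule elsewhere?** The risk sections deal with several hazards by excluding people: transmission of infection, pregnancy, claustrophobia and MRI hazards. MRI is screened with a standard form by phone and again before each scan. No exclusion or medical clearance is attached to exercise.

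**Step 3. What do the other safeguards do?** They are rest during the 6MWT, tiredness questions at each training day, a load set individually in the aerobic arm, a heart-rate monitor, supervision, emergency stops and an on-call physician. All act after enrolment. The individually set load applies to the pedaling and not to the 6MWT. The heart-rate section states no stopping threshold.

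**Step 4. Planned exposure, for context only.**

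- Pedaling per patient: 12 sessions × 30 min = 360 min. Participation ends if more than 15 sessions would be needed; if that limit refers to training sessions, the upper figure is 15 × 30 = 450 min.
- Aerobic arm: 20 patients × 12 sessions = 240 sessions; with the 16 completers assumed in Sample Size, 16 × 12 = 192.
- 6MWT: 40 patients × 2 + 20 matched controls × 1 = 100 tests.
- Matched-control training: at most 20 × 5 = 100 sessions, of unstated length.

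Totals are before any replacement of dropouts, which the plan allows. They describe how much exercise is planned and say nothing about how many people would be harmed.

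**The case against.** The strongest reply is that the phone script and the Health Questionnaire are attachments outside the public text and may well ask about heart disease, chest pain or medical advice against exercise. If they do, the fault lies in where the rule is written, and no participant goes unscreened. This stands as a limit on the claim. A reader might infer from the lists that the study does no exercise screening at all; the documents do not support that. They show only that the criteria which recruitment is said to follow do not contain it.

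Second, the authors did consider exercise risk. Under Potential Risks and Benefits, Cycling, they regard moderate recumbent cycling as generally accepted to be safe and list soreness, exertion and breathlessness. That is a fair answer for most participants doing the cycling. It does not address the 6MWT or people for whom exercise is contraindicated.

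Third, referral and letters from treating clinicians, and the radiologist's judgement of suitability, bring in people who know the patient's history. This too is fair, but it does not reach those who respond to a flyer.

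Fourth, the lists are not the only place where exclusions appear: the claustrophobia exclusion stands in the risk section. That shows a fitness rule could have been placed elsewhere, but none was found there.

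Finally, an exclusion for a known contraindication names no conditions or thresholds, so some judgement remains. That is true, but a listed criterion at least requires the question to be put to everyone, by every route.

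**Conclusion.** The concern holds in a limited form. The listed criteria for patients and for matched controls do not by themselves keep out a person with a known medical contraindication to the pedaling or to the 6MWT. This should be corrected, because the change affects who is exposed and costs little. It has no bearing on the sample-size figures.

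No number of affected people can be given, since the documents contain no prevalence of contraindications and the screening attachments are not available. The conclusion rests on the public text of the two lists and on reading the recruitment sentence as making those lists govern entry.

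Two stronger readings should be resisted. A reader might take the exposure counts as a measure of risk; they are not. A reader might also take the aerobic-arm section's mention of poor cardiovascular fitness as proof that the authors foresaw contraindicated participants. That phrase describes what the therapy is meant to improve. Being unfit is not the same as having a contraindication.

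**What to change.** Add one exclusion to the patient list, and to the healthy-control list for the matched controls aged 50–85: *known medical contraindication to moderate-intensity exercise or to the six-minute walk test*.

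Apply it in the same way to all patients, before the baseline 6MWT and before randomisation, so that it cannot operate differently once the arm is known. Apply it to matched controls before their own 6MWT. Use the phone screen, the Health Questionnaire and, for patients, the medical-record data already collected. For patients, enter the result under eligibility determination in the existing log, in which "Recruitment and screening responses from all patients contacted will be recorded in a log". If the phone script already asks the question, list it as a criterion in both places so that it binds on every route.

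The cost is two lines of text and slightly fewer eligible people. There is also a constraint on order: the Timeline puts questionnaires and gait tests in the same baseline visit and allows training on that day, so the questionnaire and record check must come before the gait tests or at an earlier contact. No new test is needed. The on-call physician, whose stated role is emergencies, need not be given a clearance role for this change.

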### **Healthy Controls:**

Inclusion criteria:

- Ages 18-85 years
- Non-Stroke Group 1 (“Matched Controls”): 50-85 years old at time of enrollment, to match the population of stroke patients to be studied
- Non-Stroke Group 2 (“Pilot Controls”): 18-50 years old at time of enrollment (Pilot subjects to be initially enrolled early in the design phase of the study, and with enrollment ongoing throughout the study to continue development.)
- No known neurologic, psychiatric or developmental disability.
- Fluent in spoken and written English

Exclusion criteria:

- Allergy to electrode gel, surgical tape, and metals.
- Subjects under treatment for infectious diseases will be excluded from the study.
- Women who are pregnant or planning to become pregnant during the course of the study will be excluded.
- Contraindications for MRI
- Age over 85 years at time of enrollment.

Persons in status relationships with members of the study team may be included in Non-Stroke Group 2 (“Pilot Controls”). Care will be taken to avoid pressuring them to participate. Such steps will include recruitment and guidance in the informed consent process only by study team members who are not in a position of influence over the potential participants.

Recruitment and screening responses from all patients contacted will be recorded in a log for assessment of recruitment yield, to be used in planning recruitment efforts for a later full-scale study. Information to be recorded will include date of contact, eligibility determination, yes/no enrollment, date of enrollment, age, sex, time since last stroke,

and stroke severity. At the conclusion of recruitment efforts for the study, all personal identifying information will be permanently discarded from this log.

***Subject Identification:***

- Through referrals by the Stroke Neurology team or any clinician involved in patient care, in the in-patient or outpatient setting.
- Clinicians involved in the care of patients may send recruitment letters to eligible patients and ascertain their interest in study participation [email text provided in IRB application].
- Candidates identified for past research in [name] group targeting upper limb therapy may be identified as candidates for this study (if they have lower-limb deficits as well). They will be identified through participant records for protocol #2015-0469 (PI: [name]), which are accessible to [name] as a Co-Investigator on that project.
- We also have permission to contact participants who have participated in other research conducted by our group ([name] 2013-1561). We propose to contact these subjects and ascertain interest in participating as a control subject in this study. Subjects who expressed a written wish not to be contacted for further research (as recorded on their Informed Consent form for protocol - #2013-1561) will be omitted.
- Databases of potential subjects maintained by the UW department of Radiology [[name] #2012-0303 Volunteer Database] may be used to identify healthy control subjects.
- By posting recruitment flyers (for subject self-identification) at different locations such as the UWHC, the School of Medicine, UW libraries, the University Station Clinic, St. Mary's hospital, Meriter hospital, Madison public libraries, stroke support and other aging support group locations, and on the web pages of Principal Investigator [name] (<http://uwbadgerlab.engr.wisc.edu>) and Co-Investigator [name] (<http://vplab.psychiatry.wisc.edu/>).
- [name], who is a radiologist and is involved in clinical imaging protocols of patients, will identify patients who are suitable for study participation as they present to the UWHC, UWMF, WIMR, or Health Emotions Research Institute (HERI) for clinical imaging.

